5.3.4 Vital signs

The parameters collected are: height (cm), weight (kg), body temperature (°C), pulse (beats per minute, bpm), systolic and diastolic blood pressure (mmHg).

The criteria for clinically notable abnormalities are defined as follows:

Clinically notable elevated values

- Systolic BP: ≥ 180 mmHg and an increase ≥ 20 mmHg from baseline
- Diastolic BP: ≥ 105 mmHg and an increase ≥ 15 mmHg from baseline
- Body temperature: $\geq 39.1^{\circ}\text{C}$
- Weight: Increase from baseline of $\geq 10\%$

- Pulse: ≥ 120 bpm with increase from baseline of ≥ 15 bpm

Clinically notable below normal values

- Systolic BP: ≤ 90 mmHg and a decrease ≥ 20 mmHg from baseline
- Diastolic BP: ≤ 50 mmHg and a decrease ≥ 15 mmHg from baseline
- Body temperature: $\leq 35^{\circ}\text{C}$
- Weight: decrease from baseline of $\geq 10\%$
- Pulse: ≤ 50 bpm with decrease from baseline of ≥ 15 bpm

The following summaries will be produced for each vital sign parameter:

- Summary statistic for change from baseline to the worst post-baseline value (in both directions, i.e. from baseline to highest post baseline and from baseline to lowest post-baseline value),
- Number and percentage of patients with at least one post-baseline vital sign abnormality (in both directions, i.e. both elevated and below normal values).

All vital sign assessments will be listed by vital sign parameter. Clinically notable values will be flagged on listings.

5.3.5 Other safety data

5.3.5.1 ECG

The following analyses will be performed for HR, PR, QT intervals and QRS duration, ventricular rate, QTcB (Bazett's formula) and QTcF (Fridericia's formula):

- Summary statistics at baseline and all scheduled post-baseline time points,
- Summary statistics of changes from baseline at each scheduled post-baseline time point,
- Listing of ECG data (scheduled and unscheduled visits).

Number (%) of patients with a notable QT interval, based on both QTcB and QTcF, and newly occurring qualitative ECG abnormalities will be summarized at all scheduled post-baseline time points. A newly occurring ECG abnormality is defined as an abnormal post-baseline finding that was not present at baseline.

Notable criteria for QTcB/QTcF include:

- > 450 ms at any post-baseline scheduled time point and ≤ 450 ms at baseline,
- > 480 ms at any post-baseline scheduled time point and ≤ 480 ms at baseline,
- > 500 ms at any post-baseline scheduled time point and ≤ 500 ms at baseline,
- An increase from baseline > 30 ms at any post-baseline scheduled time point,
- An increase from baseline > 60 ms at any post-baseline scheduled time point.

A patient with multiple occurrences of a notable QT interval or a newly occurring ECG abnormality is counted only once in that category.

Patients with notable QT interval values and newly occurring qualitative ECG abnormalities will be flagged in the listings.

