To document the changes in patient-reported outcome questionnaires (CushingQoL and WPAI-GH)	The change from baseline to Week 12, 24 and 48 in CushingQoL and WPAI-GH scores	
To document the effects of pasireotide s.c. on the GH/IGF-I axis	The change from baseline to Week 12, 24 and 48 in GH and IGF-I separately	
To document the overall safety and tolerability of pasireotide s.c. in patients with CD	Incidence of AEs, and laboratory, vital signs and electrocardiographic abnormalities. Changes in laboratory values, electrocardiograms readings, and in vital signs values.	

4 Study design

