If at any visit a QTcF > 500 msec is observed, triplicate ECGs, each 2-3 min apart need to be taken approximately 1 hour after the initial ECG. The mean QTcF from the triplicate ECGs will be determined. If the mean QTcF is > 500 msec, the patient has to discontinue the study medication until a cardiologist has re-evaluated the ECG. The re-evaluation is required to be done as soon as practical but within 7 days of the initial finding of abnormal ECG. If the cardiologist confirms a mean QTcF > 500 msec, the patient will be withdrawn from the study. Otherwise and if the cardiologist confirms that at least one ECG shows QTcF > 480 msec, the cardiac assessments described for a confirmed QTcF > 480 msec are to be followed.

If at any visit a $480\text{msec} < \text{QTcF} \leq 500\text{msec}$ is observed for the first time for a patient at a given dose level, the following steps are to be taken (as described in [Figure 6-2](#)):

- A cardiology consultation must be sought as soon as practical but within 7 days of the initial finding of abnormal ECG and the cardiologist is to re-evaluate the ECG
 - If a $\text{QTcF} > 480\text{msec}$ is NOT confirmed, no further action is to be taken
 - If a $\text{QTcF} > 480\text{msec}$ is confirmed, a cardiologist must perform a thorough examination (such as reviewing baseline ECG, concurrent medications and performing a cardiovascular examination (including at least a cardiac auscultation) to assess the patient for cardiovascular risk factors).
 - If based upon the assessment by the cardiologist, the investigator considers that there is an acute cardiovascular safety risk and that the patient should not continue with study medication, the patient is to be discontinued immediately (discontinuation criteria to be followed).
 - If following the examination by the cardiologist, the investigator considers that there is not an acute cardiovascular safety risk and that the patient could continue to receive study medication, a 24-hr Holter-ECG is to be recorded as soon as practical but within 7 days after the initial finding of abnormal ECG. The Holter ECG is to be started 30 minutes prior to an injection of study medication.
 - The results of the ECGs, cardiac examination, Holter ECG and the recommendations by the cardiologist are to be evaluated by the Investigator to determine whether the patient should continue in the trial or not (discontinuation criteria to be followed)

Figure 6-2 QT Prolongation Monitoring Flow Chart

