4.4 Visit windows

It is anticipated that some assessments could be done outside the protocol planned visit windows, for that purpose a computed Visit windows schedule is defined.

Visits after the date of first dose are scheduled weekly for the first 4 weeks and then monthly from study day 28 (visit number 6) to study day 168 (visit number 11). Thereafter every 12 weeks/84 days.

Table 4-1 Visit windows

Study visit	Week	Visit window	Visit window Start*	Visit window Mid-point*	Visit window End*	Visit window Duration
1 (Screening)	-1	-1	-21	0	-1	21
2 (Baseline)	0	0	0	0	0	1
3	1	1	1	7	11	7
4	2	2	12	14	18	7
5	3	3	19	21	25	7
6	4	4	26	28	32	7
7	8	5	33	56	70	28
8	12	6	71	84	98	28
9	16	7	99	112	126	28
10	20	8	127	140	154	28
11	24	9	155	168	182	28
12	36	10	183	252	294	84
13	48	11	295	336	378	84
14	60	12	379	420	462	84
15	72	13	463	504	546	84
16	84	14	547	588	630	84
17	96	15	631	672	714	84
18	108	16	715	756	798	84
19	120	17	799	840	882	84
20	132	18	883	924	966	84
21	144	19	967	1008	1050	84
22	156	20	1051	1092	1134	84

*Note: * study day*

For summary statistics (tables) for all laboratory data assessment visits are processed as follows:

1. Unscheduled visits are used.

2. Unless stated otherwise, the closest assessment to the mid-point of each visit-window is considered.
3. In case 2 or more assessments are reported on the same day, or have the same distance from the mid-point, i.e. 2 days before, 2 days after, then the mean will be taken.

With regard to mean 24h-UFC, the above rules do not apply as per protocol there are particular definitions, see section 5.2.1 for further details.

All lab assessments are listed.

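### Minor improvement: SAP 5.3.5.1 counts notable QTc values and new ECG abnormalities at scheduled time points only, so an any-time row should be added beside the existing counts

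*SAP*

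**What the plan says.** SAP 5.3.5.1 sets five notable criteria for QTcB and QTcF: above 450, 480 and 500 ms where baseline was at or below the same limit, and increases above 30 and above 60 ms. All five carry the same restriction; the middle threshold reads "> 480 ms at any post-baseline scheduled time point and ≤ 480 ms at baseline". The sentence that defines the table repeats it: notable QT intervals and "newly occurring qualitative ECG abnormalities will be summarized at all scheduled post-baseline time points".

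Unscheduled ECGs are assigned to one output, "Listing of ECG data (scheduled and unscheduled visits". The section adds that "Patients with notable QT interval values and newly occurring qualitative ECG abnormalities will be flagged in the listings". A newly occurring abnormality is defined as a post-baseline finding absent at baseline, with no scheduled limit in that definition; only its tabulation is limited.

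Protocol Table 3-1 makes these counts part of a secondary safety endpoint: "Incidence of AEs, and laboratory, vital signs and electrocardiographic abnormalities". It does not say which ECGs count.

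**The concern.** A threshold count of QTc values should show how many patients crossed the threshold while under observation, without relying on an investigator's judgement of significance. Restricting it to scheduled ECGs drops any patient who crosses only on an extra ECG, and extra ECGs may be taken because something prompted them.

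The SAP is more inclusive for neighbouring data. The vital-sign count in SAP 5.3.4 is of patients with at least one abnormality after baseline, with no scheduled limit. The laboratory shift tables in SAP 5.3.3 use the worst on-treatment value, and SAP 4.4 brings unscheduled visits into the laboratory tables. No reason is given for treating ECGs differently.

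At stake is some understatement of one component of a secondary safety endpoint. The primary variable (SAP 5.1.1) is based on adverse events and does not use these counts. No hypothesis is tested (Protocol 10.4.2).

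**Working it through.** The plan states no figure on this point, so there is nothing to reproduce. The check is mainly textual, followed by an illustration of scale.

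**1. Is an unscheduled ECG counted anywhere in the ECG tables?** SAP 5.3.5.1 limits the summary statistics, the changes from baseline, the five criteria and the new-abnormality count to scheduled time points. Only the listing includes unscheduled visits.

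**2. Does SAP 4.4 bring it back in?** That section opens generally: "It is anticipated that some assessments could be done outside the protocol planned visit windows". Its processing rules, including the use of unscheduled visits, are introduced by "For summary statistics (tables) for all laboratory data assessment visits are processed as follows". The explicit rule therefore covers laboratory data. The general sentence leaves some room to map an off-schedule ECG to a window. If the laboratory rules were borrowed for that purpose, they would keep the assessment closest to the mid-point of each window, so not every unscheduled value would count even then.

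**3. Is the listing flag affected?** For QTc, the flag depends on the word notable, which itself contains the scheduled limit, so an unscheduled value above 480 ms might be listed without a flag. The SAP does not settle this. For new ECG abnormalities the definition has no such limit, so the flag should work.

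**4. Which patients have another route into the tables?**
- Protocol 6.2.1.1: after a reading above 500 msec and repeat triplicates, "If the mean QTcF is > 500 msec, the patient has to discontinue the study medication until a cardiologist has re-evaluated the ECG". Under Protocol 8.1.1 a test result that forces a change in study medication is an adverse event. Protocol 8.2.2 names QT prolongation as an event of special interest, and SAP 5.3.2.1 tabulates such events.
- Protocol 7.2.2.5.1: new or worsened findings judged clinically significant are recorded as adverse events.
- For other values there is no guaranteed route. The footnote to Protocol Table 6-1 requires no dose reduction for QT prolongation, so the dose-change criterion does not by itself make these values adverse events.

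**5. Direction.** Scheduled ECGs are a subset of all post-baseline ECGs, and the baseline condition is the same. The scheduled-only count therefore cannot exceed the any-time count.

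**6. Scale.** Inputs: about 200 patients planned (SAP 4.10.1); all event counts below are assumed. The step per missed patient is 100/n percentage points: 100/200 = 0.50, and for assumed sizes of 150 and 250, 0.67 and 0.40. Exact 95% limits (Clopper-Pearson): lower = Beta quantile 0.025 with parameters (x, n − x + 1); upper = Beta quantile 0.975 with parameters (x + 1, n − x).

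| Assumed row | Scheduled only | With one further patient |
|---|---|---|
| Rare, such as above 480 ms | 3/200 = 1.5% (0.31 to 4.32) | 4/200 = 2.0% (0.55 to 5.04) |
| Common, such as increase above 30 ms | 20/200 = 10.0% (6.22 to 15.02) | 21/200 = 10.5% (6.62 to 15.60) |

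The SAP plans no interval for these rows; the limits are shown only for scale. With no such patient the two rows are identical.

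**7. Date limit for the added row.** SAP 5.3.1 ends the on-treatment period 28 days after the last dose. Protocol 7.1.2 allows the Study Completion visit at 28 ± 5 days, so as late as 28 + 5 = 33 days. Table 7-1, as extracted, does not clearly show whether an ECG is due at that visit. A row that limits only unscheduled ECGs to the on-treatment period works either way: it admits no unscheduled post-treatment ECG and drops no scheduled one.

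**The case against.** The best defence is that this is a legitimate choice. SAP 5.3.5.1 states one rule and applies it consistently, nothing in the protocol contradicts it, and a fixed schedule gives every patient comparable opportunity to qualify. Unscheduled ECGs are not taken uniformly, and ECGs are read locally. That stands, and it is why the scheduled counts should stay and the any-time row should be an addition with a footnote.

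It is also fair that no affected patient is shown to exist. Table 7-1 appears to schedule an ECG at nearly every visit, and the protocol's triplicates follow a reading already above 500 msec; if that reading was at a scheduled visit, the patient is already counted. Unscheduled ECGs are perhaps more likely after Week 24, when visits are 12 weeks apart, but the documents give no number.

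A reader might infer that the rule hides serious QT events. The documents do not support that. Confirmed values above 500 msec stop study drug and so become adverse events, and a confirmed value above 480 msec leads to a cardiologist's examination. Nor do they support reading the rule as a conflict with the protocol endpoint, which is silent on which ECGs count. What the defence does not reach is the unconfirmed or lower-threshold value that nobody judges clinically significant. A threshold table exists to capture such values, and the adverse event tables do not guarantee that they appear.

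**Conclusion.** The point holds as a minor, inexpensive improvement. On a plain reading, a patient who qualifies only on an unscheduled ECG is missing from the notable-QTc or new-abnormality row, and a notable QTc value may also be unflagged in the listing. The flagging concern does not extend to new ECG abnormalities.

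The direction is certain relative to an any-time count; the size is unknown and probably small. At 200 patients each affected patient adds 0.5 percentage points, which is visible in a rare row and negligible in a common one. The conclusion assumes that scheduled in SAP 5.3.5.1 means a planned visit and that the general wording of SAP 4.4 was not meant to map unscheduled ECGs to time points. The second assumption is the more natural reading but is not beyond dispute.

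**What to change.** Keep all existing scheduled-time-point outputs. Add to SAP 5.3.5.1:

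> In addition, the number (%) of patients meeting each QTcB/QTcF criterion, or having a newly occurring ECG abnormality, on any post-baseline ECG (scheduled or unscheduled) will be presented as an any-time row; unscheduled ECGs are included if taken in the on-treatment period (to 28 days after last dose), and all scheduled ECGs remain included.

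Flag notable QTc values in the listings whether scheduled or unscheduled, and mark those after the on-treatment period. The added row settles the matter whichever way SAP 4.4 is read.

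The cost is one sentence, one extra row per criterion and for new abnormalities, and a footnote. No new data are needed, since unscheduled ECGs are already listed. If the database is already locked, SAP section 1 provides for recording the change separately. The downside is that the any-time incidence may look slightly less favourable and that patients with more unscheduled ECGs have more chances to qualify; the footnote should say so.

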5.3 Exclusion criteria

Patients eligible for this study must not meet **any** of the following criteria:

1. Radiotherapy of the pituitary <4 weeks before screening or patient who has not recovered from side effects
2. Patients with compression of the optic chiasm causing acute clinically significant visual field defect
3. Patients with Cushing's syndrome due to ectopic ACTH secretion
4. Patients with hypercortisolism secondary to adrenal tumors or nodular (primary) bilateral adrenal hyperplasia
5. Patients who have a known inherited syndrome as the cause for hormone over secretion (i.e. Carney Complex, McCune-Albright syndrome, MEN-1)
6. Patients with a diagnosis of glucocorticoid-remedial aldosteronism (GRA)
7. Patients who have undergone major surgery within 1 month prior to screening
8. Patients with known gallbladder or bile duct disease, acute or chronic pancreatitis (patients with asymptomatic cholelithiasis and asymptomatic bile duct dilation can be included)
9. Diabetic patients whose blood glucose is poorly controlled as evidenced by $\text{HbA}_{1\text{C}} > 8\%$
10. Patients who have clinically significant impairment in cardiovascular function or are at risk thereof, as evidenced by
 - congestive heart failure (NYHA Class III or IV), unstable angina, sustained ventricular tachycardia, clinically significant bradycardia, high grade AV block, history of acute MI less than one year prior to study entry
 - QTcF >450 msec at screening
 - History of syncope or family history of idiopathic sudden death
 - Risk factors for Torsades de Pointes such as uncorrected hypokalemia, uncorrected hypomagnesemia, cardiac failure
 - Concomitant disease(s) that could prolong the QT interval such as autonomic neuropathy (caused by diabetes or Parkinson's disease), HIV, cirrhosis, uncontrolled hypothyroidism, concomitant medication(s) with known risk for TdP
11. Patients with liver disease or history of liver disease such as cirrhosis, chronic active hepatitis B and C, or chronic persistent hepatitis, or patients with ALT or AST more than

2 x ULN, serum creatinine >2.0 x ULN, serum bilirubin >1.5 x ULN, serum albumin < 0.67 x LLN at screening

12. Patients who have any current or prior medical condition that can interfere with the conduct of the study or the evaluation of its results, such as

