HbA _{1c}	D	7.2.2.4.3.	X				X		X			X	X	X	X	X	X	X	
Vitamin B12	D	7.2.2.4.3.	X					X			X		X					X	
Urinary free cortisol and urine creatinine	D	7.2.1.1.1.	X					X	X	X	X	X	X	X	X	X	X	X	
Serum cortisol	D	7.2.1.1.2.	X			X		X	X	X	X	X	X	X	X	X	X	X	
Plasma ACTH	D	7.2.1.1.2.	X		X		X	X	X	X	X	X	X	X	X	X	X	X	
HbsAg and anti-HCV	D	7.2.2.4.6.	X																
Signs and symptoms of Cushing's disease	D	7.2.1.1.3.	X	X	X	X	X	X	X	X	X	X	X	X	X	X	X	X	
Cushing's syndrome HRQoL and WPAI-GH questionnaire	D	7.2.1.1.4 7.2.1.1.5.		X				X		X			X	X	X	X	X	X	
Urinalysis	D	7.2.2.4.4.	X						X			X		X	X	X ^b	X	X	
Serum Pregnancy test	D	7.2.2.4.5.	X							X					X	X	X	X	
ECG	D	7.2.2.5.1.	X	X	X	X	X	X	X	X	X	X	X	X	X	X	X	X	
Adverse events	D	8.1.													Continuously				
Prior/Concomitant medications	D	6.3.	X												Continuously				
Drug administration	D	6.1.													Continuously				
Study phase completion record	D	7.1.3.															X		
Study completion record	D	7.1.4.																X	

	Category	Reference to Section	Screening	Baseline	Study period													Study Phase Completion	Study Completion
					1	2	3	4	5	6	7	8	9	10	11	12	13, 14,... ^a		
Visit Number																		776	777
Study Week		7.1.2.	-3 to 0	0	1	2	3	4	8	12	16	20	24	36			48, 60,... ^a	Last dose	Last dose + 4
Study days		7.1.2.	-21 to -1	0	7	14	21	28	56	84	112	140	168	252	336, 420, ^a			Last dose	Last dose + 28

^a One visit every 12 weeks/84 days until patients are transitioned to commercial pasireotide or until 31 December 2015 (until 31 December 2016 for sites in South Korea and Brazil), whichever comes first

^b To be done every 24 weeks after visit 13

D Data/assessments to be entered in the database

S Data/assessments that remain in source documents only, not to be recorded on CRF

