7.2.2.5 Cardiac assessments

7.2.2.5.1 Electrocardiogram (ECG)

[figure not shown]
A 12-lead ECG will be performed at the sites, in lying position, at all indicated visits as per [Table 7-1](#).

[figure not shown]
All ECGs should include all 12 standard leads and a Lead II rhythm strip of at least a 10-second duration. The ECGs will be evaluated locally.

Interpretation of the tracing must be made by a qualified physician and documented on the ECG CRF page. Each ECG tracing should be labeled with the study number, patient initials (where regulations permit), patient number, date, and kept in the source documents at the study site. Clinically significant abnormalities present when the patient signed informed consent should be reported on the Medical History CRF page. Clinically significant findings must be discussed with the Medical Monitor prior to enrolling the patient in the study. New or worsened clinically significant findings occurring after informed consent must be recorded on the Adverse Events CRF page. In case of confirmed QTcF $>$ 480msec, a Holter ECG will be required for patients continuing in the study (described in [Section 6.2.1.1](#)).

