4.3 Baseline definition

For efficacy and safety evaluations, *baseline assessment* is defined as the last available value (or assessment) prior to study drug start date. If for a given parameter, a patient had no value

(or assessment) prior to study drug start date, baseline will be considered missing for that efficacy and/or safety evaluation.

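### QTc increases above 30 ms are counted from one locally read ECG although two are scheduled by Visit 2, and the baseline rule may discard the Visit 2 tracing

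*SAP*

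**What the plan says.** SAP 5.3.5.1 lists the notable QTc criteria. Two are changes from baseline: "An increase from baseline > 30 ms at any post-baseline scheduled time point" and "An increase from baseline > 60 ms at any post-baseline scheduled time point". They apply to both correction formulae: "Number (%) of patients with a notable QT interval, based on both QTcB and QTcF". The count is ever/never: "A patient with multiple occurrences of a notable QT interval or a newly occurring ECG abnormality is counted only once in that category".

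The section has no baseline rule of its own, so SAP 4.3 governs. There, baseline for efficacy and safety "is defined as the last available value (or assessment) prior to study drug start date". That is one value, with no averaging.

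Protocol Table 7-1 schedules an ECG, entered in the database, at screening, at Baseline (Visit 2) and at every visit after that. Protocol 7.2.2.5.1 describes one 12-lead tracing per indicated visit and adds: "The ECGs will be evaluated locally". Under the QT guidance in Protocol 6.2.1.1, triplicates are taken only after a QTcF above 500 ms. Protocol 5.3 excludes patients with "QTcF >450 msec at screening". Protocol 6.3 describes Visit 2 as the beginning of treatment. No section says whether the Visit 2 ECG precedes the first injection.

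**The concern.** The error in one baseline tracing enters every later comparison for that patient. A chance-low reading makes each on-study ECG look raised, and the ever-count needs only one of them to cross 30 ms. A chance-high reading can hide a real rise. The study has no control arm, so nothing in the data shows how many flags would occur without drug.

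Which tracing serves as baseline is also unclear. SAP 4.3 works on dates. If the Visit 2 ECG is done before the injection but on the same day, it is not prior to the start date and drops out. The screening ECG then becomes baseline, and it has already passed a cut-off that favours low readings.

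At stake is the reported number and percentage of patients with a notable QTc increase, in a study whose primary objective is safety and which lists QT prolongation as an event of special interest (Protocol 8.2.2).

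**Working it through.** The plan states no expected rate of notable QTc increase, so there is no figure of its own to reproduce.

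**Inputs from the documents**
- Thresholds T: 30 and 60 ms (SAP 5.3.5.1).
- Baseline readings used, m: 1 (SAP 4.3). Scheduled at or before treatment start: 2 (Table 7-1).
- Scheduled post-baseline ECGs to Week 48, K: Weeks 1, 2, 3, 4, 8, 12, 16, 20, 24, 36 and 48, so 11.
- Planned size: about 200 (Protocol 10.8).

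**Assumptions, not in the documents**
- Within-patient SD of one QTc reading: 8 to 15 ms, with 20 ms as an extreme.
- Independent normal errors, no drug effect, all 11 ECGs done.

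**One comparison.** The variance of a change is SD² × (1 + 1/m): 2 SD² for m = 1 and 1.5 SD² for m = 2, a 25% cut. At SD 10 the SD of a change is 14.1 or 12.2 ms, and the chance of exceeding 30 ms is 1.7% or 0.7%.

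**Any of 11 comparisons.** The comparisons share one baseline error b, so

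P = ∫ φ(b; 0, SD/√m) × [1 − Φ((T + b)/SD)^11] db.

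The error-free column is 1 − Φ(T/SD)^11.

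| T | SD | One ECG | Mean of two | Error-free baseline | Per 200, one → two |
|---|---|---|---|---|---|
| >30 | 8 | 3.2% | 1.1% | 0.1% | 6 → 2 |
| >30 | 10 | 11.1% | 6.3% | 1.5% | 22 → 13 |
| >30 | 12 | 21.3% | 15.8% | 6.6% | 43 → 32 |
| >30 | 15 | 35.7% | 31.9% | 22.4% | 71 → 64 |
| >30 | 20 | 52.6% | 53.1% | 53.3% | 105 → 106 |
| >60 | 10 | 0.01% | 0.00% | 0.00% | 0.02 → 0.00 |
| >60 | 12 | 0.20% | 0.02% | 0.00% | 0.4 → 0.05 |
| >60 | 15 | 2.0% | 0.6% | 0.04% | 3.9 → 1.1 |
| >60 | 20 | 11.1% | 6.3% | 1.5% | 22 → 13 |

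At SD 8 the share above 60 ms is 0% either way. Above 30 ms the relative reduction is (3.20 − 1.11)/3.20 = 65% at SD 8, then 43%, 26% and 11% at SD 10, 12 and 15. From SD 8 to 12 most false flags come from baseline error. At SD 20 the maximum of 11 noisy on-study readings decides the result.

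**Allowing for the screening exclusion.** This was simulated with a further assumption (true QTcF mean 415 ms, between-patient SD 20 ms), keeping only patients with a screening reading of 450 ms or less.

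| SD | >30 ms, screening ECG only | Visit 2 ECG only | Mean of two | Bias of screening ECG | Bias of mean |
|---|---|---|---|---|---|
| 8 | 3.3% | 3.2% | 1.1% | −0.3 ms | −0.2 ms |
| 10 | 11.7% | 11.1% | 6.6% | −0.6 ms | −0.3 ms |
| 12 | 22.6% | 21.3% | 16.4% | −0.9 ms | −0.4 ms |
| 15 | 38.3% | 35.7% | 33.6% | −1.5 ms | −0.7 ms |

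The mean of two still gives fewer false flags than either single tracing.

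**Which ECG is baseline.** Table 7-1 puts Visit 2 at study day 0. SAP 4.2 makes the drug start date day 1 and says there is no day 0. Protocol 6.3 has treatment beginning at Visit 2. The documents therefore do not settle whether the Visit 2 ECG falls before or on the start date, and SAP 4.3 turns on exactly that.

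**The case against.** SAP 4.3 is clear in form and applied uniformly, and a last-value baseline is defensible as the reading closest to dosing. The within-patient SD is assumed, and the size of the effect depends heavily on it. The analysis is descriptive: no hypothesis is tested, the primary variable is adverse events, and the same section reports mean changes, which zero-mean baseline noise does not bias, and counts above absolute limits. Patient-level QT actions in Protocol 6.2.1.1 use absolute QTcF, not change. All of this stands, and it keeps the point small.

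Two practical objections also stand. A second usable pre-dose ECG is not guaranteed. Protocol 7.2.2.5.1 asks for a date on the tracing and does not mention a time. A post-dose Visit 2 ECG averaged into baseline would put drug effect there; Protocol 1.2.2 reports a QTcF peak 2 hours after dosing in the thorough QT study. Averaging also brings in part of the downward selection of the screening ECG. The simulation shows that this selection shrinks the gain but does not remove it.

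A reader might infer more than the documents support:
- That counts above 60 ms are distorted as much as those above 30 ms. Up to SD 12 at most 0.2% of patients are affected.
- That two clean pre-dose tracings exist for every patient. Table 7-1 schedules two ECGs but does not state that the second is pre-dose.
- That every Visit 2 ECG is discarded. This follows only where it was taken on the dosing day, and the documents do not say how often that is.
- That averaging removes the noise. At SD 15 about 32% are still flagged above 30 ms.

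**Conclusion.** The point holds as a low-cost improvement. The plan counts QTc increases from a single locally read ECG when a second is scheduled, and the wording of its baseline rule can exclude the later of the two. Averaging lowers the false share above 30 ms across the assumed SD range of 8 to 15 ms, by about 2 to 6 percentage points (3.2 − 1.1 = 2.1 at SD 8; 21.3 − 15.8 = 5.5 at SD 12). Shares are slightly higher for the screening-only and two-ECG baselines once the exclusion is allowed for. The gain is lost at SD 20. Above 60 ms it matters only from about SD 15.

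These sizes rest on an SD that the documents do not give, on independent normal errors and on full attendance to Week 48. No test, error rate or sample size changes; only the reported percentages do. The unclear status of a same-day Visit 2 ECG is a gap in the text that does not depend on these assumptions.

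**What to change.** In SAP 5.3.5.1, define the baseline for QTcF, QTcB, the other intervals and HR as the mean of the screening and Visit 2 ECGs recorded before the first injection. Include a Visit 2 ECG from the dosing day only where it is documented as pre-dose. Use the single value where only one ECG qualifies. Apply this baseline to the changes, to the counts above 30 and 60 ms, and to the baseline conditions attached to the 450, 480 and 500 ms criteria. Show the last-value version of SAP 4.3 as a sensitivity summary.

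The cost is a few sentences, a changed derivation, one extra summary and a check of what is recorded about the timing of Visit 2 ECGs. No new ECGs are needed. There are three downsides: the ECG baseline departs from the general rule, the mean carries part of the small downward selection of the screening ECG, and noise in the maximum of the on-study readings remains.
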